## 3Justification

Given that NAFLD currently has no FDA-approved pharmacological treatment, there is an urgent need for safe, cost-effective, and accessible interventions. A well-designed RCT is essential to establish a causal relationship between coffee consumption and liver health., determine whether coffee can be an effective dietary intervention for NAFLD management. If proven effective, this could serve as a simple, affordable, and widely accepted dietary intervention for NAFLD management. Given its accessibility and tolerability, incorporating coffee into clinical guidelines could provide a practical solution to help mitigate the economic and healthcare burden of NAFLD. Thus, the aim of our study is to prove that coffee is a safe and effective dietary intervention for managing NAFLD, with the goal of providing evidence that could shape future guidelines.

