## 2. Hypothesis, Objectives, Outcomes and End points

## 2.1. Hypothesis:

- **Null Hypothesis**: Coffee (caffeine) supplementation has no effect on hepatic steatosis and fibrosis in NAFLD patients.
- Alternative Hypothesis: Coffee (caffeine) supplementation reduces hepatic steatosis and fibrosis in NAFLD patients.

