#### **Secondary Objectives:**

- To assess changes in liver enzymes (ALT, AST, GGT) with caffeine supplementation.
- To assess the impact on metabolic markers(HbAIC, lipid profile, BMI).
- To assess potential side effects of caffeine supplementation.

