#### **Final Sample Size**

- 55 participants per group
- Total: 110 participants (both groups combined)

28.02.2025

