## 4.8. Data analysis:

Data will be analyzed using SPSS software version 21. Baseline patient characteristics will be described using descriptive statistics. Continuous variables will be expressed using mean and standard deviation or median with range depending on the distribution of data. Categorical variables will be expressed using frequency and percentage. Primary analysis will be done using a modified intention to treat (mITT) analysis where only subjects with at least one follows up assessment done will be included in the analysis.

Mean change in CAP score and LSM from baseline to 6 months will be compared between the 2 groups (Caffeine tablets vs placebo) using Independent T test or Mann Whitney U test depending on the distribution of data. For the secondary endpoints continuous variables will be compared using Independent T test or Mann Whitney U test and categorical variables will be compared using Chi square test. Repeated measures ANOVA will be used for analysis of change in variables from baseline till end of study. P value less than 0.05 will be considered statistically significant.

Safety outcomes will be described using descriptive statistics. For patients who were lost to follow up, the last available value will be used for analysis.

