#### Safety and adverse event data analysis

28.02.2025

Vital sign measurements and laboratory biochemical test data will be presented as mean and standard deviation.

A listing of all adverse events by participants including % of participants who experienced adverse events will be presented. This list will include adverse event (actual term and preferred term), event start and end dates, category as per the ICH Topic E 2 A Clinical Safety Data Management: Definitions and Standards for Expedited Reporting, relationship to study drug/procedure, seriousness, and outcome.

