#### **Risks**

There is a risk of participants experiencing side effects of caffeine such as palpitations, high blood pressure, gastrointestinal discomfort, insomnia and anxiety

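### Section 3 aims to prove that coffee is safe, but the plan describes harms without a between-arm estimate and 55 per arm was sized on efficacy alone

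*Protocol*

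**What the plan says.** - **Aim (section 3, Justification):** "the aim of our study is to prove that coffee is a safe and effective dietary intervention for managing NAFLD", with a view to informing guidelines.
- **Formal safety objective (section 2.2, secondary objectives):** "To assess potential side effects of caffeine supplementation".
- **Hypotheses (section 2.1):** efficacy only. The null is that coffee "supplementation has no effect on hepatic steatosis and fibrosis in NAFLD patients".
- **Endpoints (section 2.4):** no primary, secondary or exploratory endpoint is an adverse event or a vital sign. AST, ALT and GGT are secondary endpoints.
- **Safety analysis (section 4.8):** "Safety outcomes will be described using descriptive statistics". The safety subsection adds: "Vital sign measurements and laboratory biochemical test data will be presented as mean and standard deviation". For adverse events: "A listing of all adverse events by participants including % of participants who experienced adverse events will be presented".
- **Expected harms (section 6.1):** "There is a risk of participants experiencing side effects of caffeine such as palpitations, high blood pressure, gastrointestinal discomfort, insomnia and anxiety". No rates are given.
- **Size (section 4.4):** "55 participants per group", from an SD of 5, a difference of 3, two-sided 5% alpha, 80% power and 20% dropout.

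**The concern.** The aim in section 3 and the analysis in section 4.8 do not match. Proving safety means ruling out an excess of harm larger than some stated amount. That needs at least an estimate of the difference between arms and an upper limit for it. For adverse events and vital signs the protocol states no between-arm difference, confidence interval, margin or acceptable excess. It plans summaries and a listing.

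At stake is how far the results can be taken. The protocol looks ahead to guideline use, and a safety claim in that setting would rest on data that leave moderate excesses of the named caffeine effects, and uncommon harms of any kind, largely open.

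**Working it through.** **1. Where 55 per arm comes from.** Inputs from section 4.4: SD 5, difference 3, z-values 1.96 and 0.84, dropout 20%. The standard two-sample formula gives

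n = 2 × 5² × (1.96 + 0.84)² / 3² = 2 × 25 × 7.84 / 9 = 43.6, so 44 per arm; 44 / 0.8 = 55 per arm, 110 in total.

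The stated size is reproduced. (The formula as printed in section 4.4 does not give it; that is a separate matter.) No safety quantity enters the calculation.

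**2. What zero events would mean.** With no event of a given type among n patients, the one-sided 95% upper bound on the risk is 1 − 0.05^(1/n). For n = 55: 1 − 0.05^(1/55) = 5.3%.

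**3. Chance of seeing no case at all.** (1 − p)^55 for a true risk p:

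| True risk on caffeine | Probability of no case in 55 |
|---|---|
| 1% | 58% |
| 2% | 33% |
| 5% | 6% |

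**4. What a between-arm comparison could show.** The protocol gives no adverse event rates, so the rates here are assumptions. Power of a two-sided 5% chi-square test at 55 per arm, by exact enumeration of the two binomial distributions:

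| Placebo vs caffeine | Power |
|---|---|
| 5% vs 15% | 42% |
| 10% vs 20% | 31% |
| 10% vs 30% | 77% |

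By the usual normal approximation, power to detect a doubling is 9%, 17%, 31% and 63% for placebo rates of 2%, 5%, 10% and 20%. Section 4.8 does not plan this test for harms. The figures show how much information the sample holds, not how a planned test performs.

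**5. Width of the interval proposed under the fix.** With equal rates p in both arms, the 95% half-width of the risk difference is 1.96 × √(2p(1 − p)/55): 5, 8, 11 and 15 percentage points for p = 2%, 5%, 10% and 20%. At a 10% rate, for example, an observed difference of zero leaves an excess of up to about 11 points open.

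**6. What is already compared between arms.** AST, ALT and GGT are secondary endpoints (section 2.4), and section 4.8 compares continuous secondary endpoints between groups by t-test or Mann-Whitney test. The missing comparison therefore concerns adverse events and vital signs.

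**The case against.** The strongest reply is that the phrase stands in a rationale, while the parts of the protocol that carry inference are modest. The formal objective is to assess side effects, no hypothesis concerns safety, and descriptive reporting fits that objective and is normal in a trial sized on efficacy. Intervals and table layout could also be left to a statistical analysis plan. Much of this stands, and it is why the point is minor. It does not remove the point. Section 3 presents the phrase as the aim of the study, and the protocol itself fixes the descriptive method, so claim and method conflict within one document.

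A reader might go further and infer that the absence of a visible signal will be reported as proof of safety. The documents do not say so. No decision rule or success criterion turns an unremarkable safety table into a conclusion.

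A reader might also infer that no safety-relevant variable is compared between arms, or that only 44 per arm inform safety. The liver enzymes contradict the first. As to the second, adverse events are collected from consent (section 7.4) and asked about monthly (section 4.6), so participants who later drop out still contribute data.

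Nor would every harm be missed. A large excess of a common effect would usually be detected.

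The individual stopping criteria (section 7.7) and the safety board (section 7.8) are real protections for participants. They are monitoring, however, and put no bound on an excess risk.

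**Conclusion.** The point holds as a mismatch between the stated aim and the stated method. The trial can test efficacy and estimate tolerability; it cannot prove safety. The zero-event bound of 5.3% and the 33% chance of seeing no case of a 2% harm depend only on 55 caffeine patients being observed. The power figures of about 31% (10% vs 20%) and 77% (10% vs 30%) rest on assumed event rates and on a test that the protocol does not assign to harms. Severity is minor: the efficacy analysis is unaffected, and the formal objective in section 2.2 is already worded suitably.

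**What to change.** 1. **Section 3.** Replace the statement about proving coffee safe and effective with wording that the trial tests efficacy and estimates tolerability, in line with section 2.2.
2. **Section 4.8.** State that the following will be reported by arm, with the caffeine-minus-placebo difference and its 95% confidence interval, in all participants who took study tablets: the proportion with any adverse event; the proportion with each caffeine effect named in section 6.1; and change in blood pressure and heart rate.
3. **Section 4.8, interpretation.** Add that an unremarkable or non-significant comparison is not evidence of safety, and that the upper confidence limit shows the excess that the trial has not excluded. No margin is needed for this, because no safety claim is then made.

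The cost is a few sentences and a few table columns. Adverse events, blood pressure and heart rate are already recorded at the monthly visits (sections 4.6 and 5.5), so no extra patients, visits or measurements are needed. The price is a more modest safety claim.

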#### 1.2. Supplementation of Caffeine in Liver conditions

Specifically, coffee has demonstrated beneficial effects on liver-related conditions. Regular coffee consumption has been linked to a reduced risk of cirrhosis and chronic liver disease, a lower severity of viral liver diseases (e.g., hepatitis C) and decreased levels of liver enzymes (ALT, GGT, bilirubin), indicating improved liver function(14,15).

These protective mechanisms of coffee are thought to stem from its antioxidant, anti-inflammatory, and anti-adipogenic properties (16). Coffee consumption has been associated with reduced production of reactive oxygen species (ROS), inflammatory cytokines (TNF- $\alpha$ , TGF- $\beta$ ), and oxidative stress, thereby protecting hepatocytes from damage(17). It has also been associated with the inhibition of hepatic stellate cell activation, thereby reducing liver fibrosis(18). Moreover chlorogenic acids, which is a constituent of coffee, also improve glucose metabolism, reduce insulin resistance, and help mitigate the risk of NAFLD progression(19).

Several studies have suggested an inverse relationship between coffee consumption and NAFLD prevalence and severity. A study reported that individuals who drank coffee regularly had a 29% reduced risk of developing NAFLD and a 30% lower risk of liver fibrosis in NAFLD patients compared to non-coffee drinkers(20,21). Experimental studies have also shown that coffee upregulates mitochondrial and endoplasmic reticulum (ER) chaperone proteins, such as glucose-related protein 78 (GRP78), which modulates ER homeostasis and prevents metabolic stress-induced liver injury(22). Coffee's polyphenols, which have a structure similar to silymarin (a known hepatoprotective compound), can increase the production of antioxidant proteins such as periredoxin-1 (PRDX-1), which helps counteract oxidative damage in hepatocytes(23).

28.02.2025

Additionally, non-caffeine components of coffee, such as cafestol, kahweol, and chlorogenic acid, have been shown to reduce triglyceride and cholesterol deposition in hepatocytes. And prevent hepatocellular carcinoma development(24).

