#### 3.1. Justification for Use of Placebo:

The use of a placebo is necessary to control the psychological effects of caffeine supplementation, ensuring that observed effects were solely due to the active ingredient. By employing a Quadruple-blind design, the placebo also would help eliminate bias.

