## 5. Intervention, Monitoring of compliance to treatment

Caffeine tablets and placebo tablets required for the trial would be sourced from Nutricost, a U.S.-based company that specializes in high-quality dietary supplements. Nutricost products are manufactured in GMP-compliant facilities and undergo third-party testing to ensure purity and consistency. The caffeine tablets specifically contain caffeine anhydrous, a dehydrated form of caffeine that provides a standardized and effective dosage and placebo are manufactured using starch ensuring that it is inert and does not affect the study's outcomes.

The study groups will receive one bottle on the day of allocation, and it will contain either caffeine tablets or placebo required for a month. The test group will receive the caffeine tablet while the control group will receive the placebo .Tablet bottles will be issued to participants according to their random number mentioned in the Case Report Form (CRF).

Patients will be asked to take the medication every day after dinner. Recommended dose and directions for use will be given verbally when dispensing the tablet pack, and written instructions will be clearly mentioned on the label of the bottle in Sinhala, Tamil and English. The patients will be asked to take the tablets home. At each monthly visit, the participants will be asked to bring tablet bottles with balance tablets, to count at the monthly visit to assess compliance. The required tablets for next month will be issued during this visit.

Participants who have < 80% compliance will be re-educated on the importance of daily administration of investigational product, as much as possible: with the overall aim to maintain  $\ge$  80% compliance over the study period.

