#### **5.2.** Dietary measurements

All patients will be instructed on a balanced diet, including decreased intake of saturated and trans fats and increased intake of fiber. In overweight patients, dietary intervention will focus on a calorie restricted diet, attained over a 6-month period. The calorie-restricted diets will be planned to create a deficit of 500- 1000 kcal/day and will be individualized for each study subject. A culturally validated Food Frequency Questionnaire (FFQ) will be used to obtain habitual intake of calories, macronutrients and micronutrients. This will be assessed monthly to monitor dietary measurements of participants.

Medical RA will meet individual patients for counselling on dietary intervention. All patients are asked to maintain food logs and ask to bring it on follow up visits and food logs will be reviewed monthly, and diet plans will be adjusted as needed.

Dietary measurements will be monitored at the baseline and during each follow up monthly visits.

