# 11.10. Annexure 1F

# **Front Label**

# **Participant ID:**

**Random Number:** 

Contents: 60 capsules (200mg each)

**Ingredients:**Caffiene anhydrous

Suggested use: Take two capsules daily after dinner

This recommended dose of this product contains as much caffeine as 4 cups of coffee. Do not consume more than 400 mg of caffeine from any source in a 24 hour period. It may cause nervousness, irritability, sleeplessness and occasional rapid heart rates. In case of accidental overdose, seek professional assistance or contact a poison control center immediately

Storage: Store in a cool, dry place away from sunlight

Warnings: Keep out of reach of children. Do not use if the seal is broken.

Manufactured by: Nutricost

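### The trial tests caffeine anhydrous but claims to prove that coffee works, and the assigned intake alone reaches the label's any-source caffeine limit, which the diet and case report form text does not follow through

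*Protocol*

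**What the plan says.** **The claim.** Protocol section 3 (Justification) argues that "A well-designed RCT is essential to establish a causal relationship between coffee consumption and liver health" and then states that "the aim of our study is to prove that coffee is a safe and effective dietary intervention for managing NAFLD", with a view to shaping guidelines. The title, the hypotheses (2.1) and the primary objective (2.2) name the intervention as coffee with caffeine in brackets.

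**The product.** Section 5 says: "The caffeine tablets specifically contain caffeine anhydrous, a dehydrated form of caffeine". On the comparator it says "placebo are manufactured using starch ensuring that it is inert and does not affect the study's outcomes". Section 3.1 justifies the placebo as "ensuring that observed effects were solely due to the active ingredient".

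**Coffee is more than caffeine.** Section 1.2 states that "non-caffeine components of coffee, such as cafestol, kahweol, and chlorogenic acid, have been shown to reduce triglyceride and cholesterol deposition in hepatocytes". It also credits chlorogenic acids with metabolic benefit, and reports that filtered coffee but not espresso was associated with less fibrosis, with composition depending on preparation.

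**Total intake.** The front label in Annexure 1F describes 60 units of 200 mg, two to be taken daily, equates the daily amount to four cups of coffee, and warns: "Do not consume more than 400 mg of caffeine from any source in a 24 hour period". Section 4.7, however, says that bottle labels carry only the random number and the directions for taking the tablets.

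**Background caffeine.** The only caffeine-related exclusion in 4.3.2 is sensitivity to it. The diet advice in 5.2 covers fats, fibre and calories. The food frequency questionnaire (FFQ) there is meant "to obtain habitual intake of calories, macronutrients and micronutrients". General food logs are reviewed monthly. The case report form (Annexure 1C) has alcohol and smoking fields but none for coffee, tea or caffeine.

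**The concern.** Two things do not fit together.

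First, the exposure named in the conclusion is not the exposure tested. A caffeine-versus-starch comparison answers a question about caffeine. If caffeine reduced steatosis, coffee might do more, less or something different, because the other components that section 1.2 considers active are not part of the described product. If caffeine did nothing, coffee could still work. A statement to guideline bodies that coffee is or is not effective would rest on an exposure nobody in the trial was assigned.

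Second, the label sets a ceiling on caffeine from all sources that the assigned intake already reaches. Yet the protocol sections on eligibility, diet and follow-up give no instruction on coffee or tea and name no item to record them. Alcohol, which is not under test, gets an intake limit and a monthly questionnaire (5.4). At stake are consistency with a safety warning printed in the protocol's own annexure, and the ability to say afterwards how much caffeine each arm actually took.

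**Working it through.** **Step 1. Reproduce the assigned intake.**

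- Annexure 1F: 2 units a day × 200 mg = 400 mg a day. The patient card (Annexure 1E) also says 400 mg.
- Check on supply: 60 units ÷ 2 a day = 30 days, which agrees with section 4.7.

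**Step 2. Room under the label limit.**

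- Limit 400 mg − assigned 400 mg = 0 mg.
- The label equates 400 mg to 4 cups, so 400 ÷ 4 = about 100 mg per cup.

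| Ordinary coffee, cups a day | Caffeine arm, mg | Over the limit, mg | Placebo arm, mg | Difference between arms, mg |
|---|---|---|---|---|
| 0 | 400 | 0 | 0 | 400 |
| 1 | 500 | 100 | 100 | 400 |
| 2 | 600 | 200 | 200 | 400 |
| 3 | 700 | 300 | 300 | 400 |

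Two cups put a caffeine-arm participant at 600 ÷ 400 = 1.5 times the limit.

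**Step 3. What happens to the randomised contrast.** Take participants who habitually drink two cups (200 mg). This is an assumption for illustration, since the protocol gives no background intake.

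- Both arms give up coffee: 400 − 0 = 400 mg.
- Neither arm does: 600 − 200 = 400 mg.
- Only the caffeine arm gives it up: 400 − 200 = 200 mg.
- Only the placebo arm gives it up: 600 − 0 = 600 mg.

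The contrast moves only in the last two cases, when behaviour differs by arm. The documents neither show that this will happen nor name the data that would reveal it.

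**Step 4. Set claim and exposure side by side.**

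| Place in the protocol | Exposure named |
|---|---|
| Section 3 (causal target and aim) | coffee |
| Title, 2.1, primary objective in 2.2 | coffee, with caffeine in brackets |
| Secondary objectives in 2.2, sections 3.1, 3.2 and 6.1 | caffeine |
| Section 5, Annexures 1E and 1F | caffeine; anhydrous form in section 5 and 1F |

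The design isolates the active ingredient, as 3.1 says. Section 1.2 describes coffee as that ingredient plus others with effects on the liver. The step from caffeine to coffee is therefore contradicted by the protocol's own background section.

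**The case against.** The best defence has four parts.

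- **The tested exposure is clear.** Most operational text says caffeine, and the coffee claim is concentrated in the rationale. This is right, and it makes the correction easy. It does not rescue the stated aim, and the bracketed wording reaches the title, the hypotheses and the primary objective.
- **The label is itself a limit.** This is also right. It would be wrong to say that the trial places no limit on other caffeine: taken with the assigned intake, the label leaves room for none. The defect is that the body text does not carry the limit through, and that 4.7 leaves open whether participants see the warning at all.
- **Intake may be captured anyway.** The FFQ is scheduled at enrolment, allocation and every monthly visit, and food logs are kept. Either may list beverages; the FFQ's items are not annexed. The participant information sheets were not available to me and may contain a coffee instruction, and section 5 adds verbal directions at dispensing. So one can say only that the text shown names no such item or rule.
- **Randomisation protects the comparison.** It balances habitual intake on average, and Step 3 shows the same 400 mg contrast whether both arms obey the label or neither does.

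A reader might infer that the contrast is unknown, that the trial compares caffeine with coffee withdrawal, or that power is lost. The documents do not support these readings. Under a shared label, drinkers in both arms would give up coffee. That the two arms carry the same warning is itself only inferred from one specimen label. No figure in the protocol allows an estimate of attenuation.

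**Conclusion.** The point holds in two parts.

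1. The claim that the trial will prove coffee safe and effective exceeds what caffeine anhydrous against starch can show, whichever way the result falls. This rests on the protocol's own text and needs no assumption.
2. The assigned intake uses all of the label's 400 mg any-source limit. On the label's equivalence, each cup of coffee adds about 100 mg above it for a caffeine-arm participant. The eligibility, diet and case report form text does not follow this through, and 4.7 and Annexure 1F disagree on what the bottle shows.

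The size of the second part in practice depends on how many participants drink coffee or tea and how much, which the documents do not give. This is not a finding of baseline bias or of a faulty randomised comparison: the caffeine contrast is 400 mg a day unless background intake shifts differently between arms. The harm is to the conclusion, to consistency with the label's warning, and to describing the exposure delivered. It should be corrected before recruitment, because intake before treatment is hard to recover once dosing has begun.

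**What to change.** - **Wording.** Restate the title, hypotheses, objectives and section 3 as caffeine anhydrous versus placebo. Drop the statement that the trial proves coffee effective and the guideline aim built on it. Coffee can remain as background motivation.
- **Recording.** Make sure that the FFQ records coffee, tea and other caffeine sources at the visits where it is already planned, and report caffeine intake by arm at baseline and during follow-up. This shows whether intake moved differently between arms.
- **Reconciliation.** Bring sections 4.7, 5 and 5.2, Annexure 1F and the participant information into agreement on total caffeine intake and on what the bottle label shows. Which rule applies is for the clinical team; no intake or dose is proposed here.

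The cost is a narrower claim, a few more questionnaire items and a text amendment. No extra visits or participants are needed, and the randomised comparison itself is unchanged.
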